Objectives (Primary, Secondary)	
Primary objective:
 
 1. Describe the clinical management in asthmatic patients in the influential area of Hospital Universitario Virgen de la Victoria according to the assistance quality indicators established by GEMA guidelines (Appendix 1), which are the following: 
 • Diagnostic confirmation by spirometry with test bronchodilator. The diagnostic confirmation of the patients with asthma is done with spirometry and bronchodilator test as an objective measure of functional impairment.

	
 • Sensitization study in allergic asthma. To patients with suspicion of allergic asthma should be performed a study of possible sensitization to different allergens. • Smoking cessation. It is recommended smoking cessation to smokers with asthma. • Educational plan in patients with asthma. Patients with asthma must follow a basic education program (formed by: knowledge about their illness, about their treatment, action plan and inhalation technique, documented in writing) as part of their treatment. • Treatment of choice in persistent asthma. The treatment of choice in persistent asthma includes inhaled glucocorticoid (IGC) used daily. In some justified cases, alternative treatment with leukotriene receptor antagonists can be considered. • Asthma treatment in pregnant women. In asthma maintenance treatment in pregnant woman is recommended to keep the commonly used drugs (agonists β2-adrenergic and inhaled glucocorticoids). • Periodic follow-up of patients. Necessity to make periodic monitoring of patients, even if they have not suffered exacerbations, through scheduled medical visits. • Periodic record of exacerbations. The specific assessment of exacerbations is evaluated periodically. 
Secondary objectives:
 
 1. To describe the sociodemographic and clinical characteristics of the study population. 2. To describe the treatment patterns (maintenance treatment, reliever treatment, type of treatment) during the last year. 3. To describe the disease control level in the study population. 4. To describe the use of resources (emergency visit, Primary care visits, specialist visits) during the last year. 5. To describe the number of patients with discontinuation of SABA within the last year and the potential impact on disease control level and use of resources. 
For descriptive purposes, an analysis of the objectives will be made based on the

--	--

	level of disease control.
Study Design	Cross-sectional cohort, non-interventional, descriptive and unicentric
Study Population and Sampling Methods	
It is planned that a total of 300 patients with asthma will be included in the study.
 
 - Target enrollment/ sample size: 300 patients approximately. - Anticipated rate of enrollment: 6 months. - Estimated study start date: September - Estimated study completion date: March
Data Source	Patient's electronical medical chart
Data Analysis Methods	
Data analysis will be performed using SAS Enterprise Guide Version 7.1 and a statistical analysis plan will be designed and agreed before the data analysis initiation.
 
All the analyzes will be performed by descriptive statistical methods of all the variables separately.
 
The quantitative data will be described by the following statistical parameters: number of valid patients (N valid), number of missing data (N missing), mean, SD, median, minimum, maximum and according to the distribution of the analyzed variable, quartiles will also be presented (percentiles 25 and 75).
 
The qualitative data will be presented through the length-frequency distributions (absolute and relative). For both cases, the following will be specified: number of observations (N) and number of missing data (N missing).

Sample Size and Power	
In order to estimate a proportion of 50% (maximum variability), with a margin of error of +/- 6 percentage points and a confidence level of 95%, a sample size 267 patients will be required. Assuming 10% of patients with non-available data from the medical records, total sample size must be 300 patients.
 
The study sample size must allow the estimation of dichotomic variables and to determine the percentage of compliance of each quality care indicator established by the GEMA guidelines. This percentage will allow to establish the degree of compliance of each group of indicators in the site.

Limitations	Cross-sectional study, missing data in clinical records

TABLE OF CONTENTS

1. INTRODUCTION / BACKGROUND	8
2. OBJECTIVES	10
2.1. Primary	10
2.2. Secondary	10
3. RESEARCH METHODOLOGY	11
3.1. Study Design	11
3.2. Study Population	12
3.2.1. Eligibility criteria	12
3.2.1.1. Inclusion criteria	13
3.2.1.2. Exclusion criteria	13
3.2.2. Sampling	13
3.3. Data Source / Data Collection	13
3.3.1. Endpoints	14
3.3.1.1. Primary endpoint	14
3.3.1.2. Secondary endpoints	14
3.4. Sample Size / Power Calculations	17
3.5. Hypotheses	18
4. DATA ANALYSIS CONSIDERATIONS	18
5. LIMITATIONS	21
6. STUDY CONDUCT, MANAGEMENT AND ETHICS	21
6.1. Ethics Committee / IRB Approval	21
6.2. Informed Consent	22
6.3. Data Protection	22
6.4. Personally Identifiable Information (PII)	23
6.5. Adverse Event (AE), Pregnancy Exposure and Incident Reporting	24
6.5.1. Definitions of adverse events	25
7. EXTERNAL INVOLVEMENT	25
7.1. Third Party Supplier	25
7.2. External Expert / Health Care Professionals	25

Appendix 4: Research team	
BIBLIOGRAPHY	32

ABBREVIATIONS

ACT	Asthma Control Test
BMI	Body Mass Index
DMP	Data Management Plan
ED	Emergency Department
ECRHS	European Community Respiratory Survey
eCRF	Electronic Case Report Form
GCP	Good Clinical Practice
GDPR	General Data Protection Regulation
GEMA	Guía Española para el Manejo del Asma
GINA	Global Initiative for Asthma
HRQoL	Health-Related Quality of Life
IC	Informed Consent
ICH	International Conference on Harmonisation
IEC	International Ethics Committee
IGC	Inhaled glucocorticoid
IRB	International Review Board
OCS	Oral Corticoids
PBD	Post Bronchodilator
SAP	Statistical Analysis Plan

1. INTRODUCTION/BACKGROUND

Asthma is a heterogenic chronic disease characterized by acute symptomatic episodes of varying severity, including intermittently inflammation and narrowing of the airways in the lungs. The prevalence of this disease is high as affects more than 300 million people worldwide, which varies by country. In Spain, the prevalence it is estimated to be around 5%, ranged between 1% in Huelva and 4,7% in Albacete, according with the European Community Respiratory Survey (ECRHS), and seems to be increased due to a higher rate of asthma diagnosis¹.

It's important to note that in this condition there is a substantial proportion of patients with inadequate control of their disease, which conducts to a higher morbidity and mortality². The poor disease control is associated to an important negative impact in patient's health-related quality of life (HRQoL), causing them daily activity impairment, loss of work productivity and the need of using unscheduled doctor visits and hospital services^{3, 4}. The direct and indirect costs in patients with a poor disease control represents an important proportion of the total cost of asthma, which it's estimated to be around 1-2% of the total public healthcare resources in developed countries, especially in patients with severe-persistent asthma^{4, 5}.

The facts previously exposed turns this disease into a major public health problem due to its high prevalence within all age and sex groups and the high proportion of uncontrolled patients, which causes a high health burden to the National Health System, and which affects directly on the affected patients, as well as their families and the society⁶.

For this reason, during the past decades multiple clinical practice guidelines have been designed to improve the quality of care in patients with asthma and to reduce the high public burden associated to this disease⁷. International guidelines such as the Global Initiative for Asthma (GINA) and national guidelines as Guía Española para el Manejo del Asma (GEMA) in Spain, both of them stating that a good disease control can be achieved by most of asthma

patients, were launched to increase the technical training of health professionals in order to reach a better disease management and conduct to a better quality of life in these patients^{8,9}.

Specifically, GEMA guidelines also includes a tool to assess the level of assistance quality care through 8 indicators covering 4 dimensions: diagnose, non-pharmacological treatment, pharmacological treatment, monitoring.

However, since guidelines have been launched, there's still evidence of high proportion of patients with poorly disease control and large impact in patient's health-related quality of life¹⁰. Despite the availability of therapeutic recommendations through guidelines, clinical studies have shown that there's poor adherence to guidelines goals³. The Asthma Insight and Reality surveys, which were performed in several regions worldwide, concluded that all participating countries didn't met GINA goals. Specifically, in Central and Eastern Europe, the results showed a high proportion of asthma population who described physical activity limitations (68,2%) and acute symptoms during the previous 4 weeks (74%). Regarding disease monitoring, it's important to note that the results demonstrated that a 36,2% of asthmatic patients had never performed a lung function test¹¹. A recent study conducted in Spain and Italy also evidenced a generally poor disease control, with around 50% of participant patients being considered uncontrolled¹², and that strategies were needed to improve the management of this disease as it was concluded in a study performed in Spain to assess the disease control according to GINA criteria¹³.

In terms of costs, it's estimated that around 70% of the total cost of the disease is determined by this poor control and management¹⁴. An adequately disease management based in a higher use of preventive anti-inflammatory medication, a better education in asthma patients and an accurately follow of the recommendations of guidelines would result in a greater disease control and in a reduction of associated costs^{15, 16, 17}.

This evidence raises the need to determine the assistance quality care in asthma population in the influential area of Hospital Universitario Virgen de la Victoria through the assistance quality

care indicators established by GEMA guidelines. The aim of this study is to obtain clinical data that allow to assess assistance quality degree in order to find improvement opportunities to achieve a better control of asthmatic patients within this influential area.

2. OBJECTIVES

2.1. Primary objective:

- To describe the clinical management in asthmatic patients in the influential area of Hospital Universitario Virgen de la Victoria according to the assistant quality indicators established by GEMA guidelines (Appendix 1), which are the following:
 - Diagnostic confirmation by spirometry with test bronchodilator. The diagnostic confirmation of the patients with asthma is done with spirometry and bronchodilator test as an objective measure of functional impairment.
 - Sensitization study in allergic asthma. To patients with suspicion of allergic asthma should be performed a study of possible sensitization to different allergens.
 - Smoking cessation. It is recommended smoking cessation to smokers with asthma.
 - Educational plan in patients with asthma. Patients with asthma must follow a basic education program (formed by: knowledge about their illness, about their treatment, action plan and inhalation technique, documented in writing) as part of their treatment.
 - Treatment of choice in persistent asthma. The treatment of choice in persistent asthma includes inhaled glucocorticoid (IGC) used daily. In some justified cases, alternative treatment with leukotriene receptor antagonists can be considered.
 - Asthma treatment in pregnant women. In asthma maintenance treatment in pregnant woman is recommended to keep the commonly used drugs (agonists β_2 -adrenergic and inhaled glucocorticoids).
 - Periodic follow-up of patients. Necessity to make periodic monitoring of patients, even if they have not suffered exacerbations, through scheduled medical visits.

- Periodic record of exacerbations. The specific assessment of exacerbations is evaluated periodically.

2.2. Secondary objectives:

- To describe the sociodemographic and clinical characteristics of the study population.
- To describe the treatment patterns (maintenance treatment, reliever treatment, type of treatment) during the last year.
- To describe the disease control level in the study population.
- To describe the use of resources (emergency visit, Primary care visits, specialist visits) during the last year.
- To describe the number of patients with discontinuation of SABA within the last year and the potential impact on disease control level and use of resources.

For descriptive purposes, an analysis of the objectives will be made based on the level of disease control.

3. RESEARCH METHODOLOGY

3.1. Study Design

A non-Interventional, descriptive, cross-sectional and unicentric study, has been designed and will be conducted in a Spanish hospital of Málaga. The design of the study imposes an only visit to be performed to obtain the patient's signed IC and after signing it (if patient agreed to participate in the study), to perform an Asthma Control Test (ACT) (Appendix 2). Except for this study visit, the rest of study will be based on electronic medical chart review of approximately 300 asthma patients belonging the influential area of Hospital Universitario Virgen de la Victoria. This chart review will be performed by the site investigator or collaborators.

The data collection is stated in 6 months, and during this period the investigators will identify and randomly include the patients who meet selection criteria to avoid bias during patient's

inclusion. The observational period will be conformed of 12 months, and the patient's data will be collected or documented in an electronic case report form (eCRF), which will automatically create or assign an identification numerical code to every patient the moment it's created in the electronic platform. This system guarantees the anonymization of each patient included in the study as no identifiable information won't be able to be captured.

[figure not shown]

Figure 1. Overall Study design

3.2. Study Population

The study will be performed in Hospital Virgen de la Victoria, which it's the reference hospital that usually attends the asthma population of its influential area. Only patients that meet the eligibility criteria will be included in the study, and it is planned that a total estimation of 300 patients with asthma diagnose will be included in it. The whole patients will be recruited by the site investigator and collaborators, who will conduct the subject's medical chart review. Before the patient's study inclusion, the investigator team must have been obtained the signed informed consent (appendix 3) of each patient recruited and according to ICH GCP and to local legal requirements.

- Target enrollment/ sample size: 300 patients.
- Anticipated rate of enrollment: 6 months.
- Estimated study start date: September 2020
- Estimated study completion date: March 2020.

3.2.1. Eligibility Criteria

All the inclusion and exclusion criteria will be reviewed by the site investigator and collaborators to ensure that the patient is eligible to be included in the study. In order to be eligible to participate in this study, prior to the inclusion, every subject must meet the following selection criteria:

3.2.1.1. Inclusion Criteria

1. Patient with written informed consent prior to participation.
2. Patient female or male ≥ 18 years of age
3. Patient with asthma diagnosis more than one year before the study inclusion
4. Clinical data available at least 1 year before the study inclusion in the electronic medical records.

3.2.1.2. Exclusion Criteria

1. Patient's participation in any clinical trial during the year prior to the index date for data collection.

3.2.2. Sampling

An estimation of 300 asthma patients belonging to the influential area of the Hospital Universitario Virgen de la Victoria will be enrolled.

3.3. Data Source / Data Collection

The data source represents the information contained in original electronic medical documents and records (source documents) that will be necessary for the study. Primary and secondary endpoints will be collected from the patient's source documents, which will be the subject's medical chart. All the study data must be obtained from the source documents.

During the 6 months of data collection period, the study variable will be gathered in an electronic case report form (eCRF), especially designed for the study and where each investigator will access through a personal user account, which will be created once the investigator assigns a personal password during the first access to the eCRF. Is responsibility of the investigator to collect all the study variables in the eCRF, from which the study data will be analyzed.

Given the possible unavailability of certain variables, there will be the possibility in the eCRF to select the unavailability of the variables in the medical records. In order to avoid missing and/or mistaken data, it will include filters and programmable edits that will give feedback when data is missing, out of range or illogical. A data management plan (DMP) will be developed to describe all processes and specifications for data handling.

The investigator/institution will facilitate study-related monitoring, audits, IRB/IEC reviews and regulatory inspection(s), providing direct access to all related source data and source documents.

3.3.1. Endpoints

3.3.1.1. Primary Endpoint

1. The primary endpoint of this study is the asthma management of the study population according to GEMA healthcare quality indicators previously defined. For this assessment, it will be determined the following calculations:
 - I. Percentage of asthmatic patients diagnosed using spirometry and bronchodilator (PBD) test.
 - II. Percentage of patients with a diagnosed history of suspected allergic asthma included in a sensitization study with different allergens.
 - III. Percentage of asthmatic smokers with documented recommendations for smoking cessation.

- IV. Percentage of patients included in an educational plan.
- V. Percentage of patients in treatment for persistent asthma* receiving inhaled glucocorticoids (ICS).
- VI. Percentage of pregnant women (if applicable) with asthma who maintain their treatment plan based on B2-adrenergic agonists and inhaled corticosteroids among the total pregnant asthmatic women recruited in the study.
- VII. Percentage of scheduled monitoring visits per patient and per year during the previous year among asthmatic patients with asthma monitored per year.
- VIII. Percentage of asthmatic patients with evaluation and documentation of exacerbations.

** Persistent asthma can have asthma symptoms on more than 2 days per week and nighttime awakenings once or twice each month.*

3.3.1.2. Secondary Endpoint(s)

- Demographic characteristics.
 - Age
 - Gender: male, female.
 - Ethnicity: Caucasian / Hispanic / African / Asian / Other / Unknown
 - Weight (kg) and height (cm): BMI autocalculated by the eCRF.
 - Pregnancy status (yes/no)
 - Smoking status (current smoker, ex-smoker*, non-smoker)
- **It will be considered that the patient is ex-smoker since the 6 months of non-smoking.*
- Clinical characteristics:
 - Age at asthma diagnosis
 - Spirometry and bronchodilator test at diagnose
 - Patient's derivation: primary care / specialized healthcare

- Asthma severity degree according to GEMA guidelines: Mild intermittent, Mild persistent, Moderate persistent and Severe persistent.
- Asthma disease control level according to:
 - Clinical criteria (number of SABA canisters retired from the pharmacy in the previous year, number of OCS retired from the pharmacy in the previous year, number of emergency service visits in the previous year, number of unscheduled primary care visits in the previous year).
 - Asthma Control Test (ACT) (most recent value available): No / Yes, specify score: ACT \geq 20 points (controlled) / ACT less than 20 uncontrolled.
- History of allergic asthma (or suspected): No / Yes.
- Sensitization to allergen study (for those patients with a diagnosed history of suspected allergic asthma).
- Registration of asthma education programs performed (last asthma education program performed by the patient): year when it was performed.
- Current asthma therapeutic level according to GEMA stepwise therapy (at patient's inclusion date): Step 1 / Step 2 / Step 3 / Step 4 / Step 5 / Step 6.
- Comorbidities (at patient's inclusion date) according to Charlson Comorbidity Index (autocalculated). A list of diseases will be displayed in order to be selected those the patient suffers at the inclusion date. The Charlson Comorbidity index score will be autocalculated automatically by the eCRF.
- Maintenance/long-term and reliever treatment prescribed for asthma (at inclusion date): type (SABA, LABA, GCI, LTRA, Biologic, immunomodulator, others), initiation date, end date or if its ongoing. Maintenance/long-term and reliever treatment prescribed for asthma in pregnant women (at inclusion date): type (SABA, LABA, GCI, LTRA,

Biologic, immunomodulator, others), initiation date and end date or if its ongoing.

- Record of scheduled monitoring asthma visits in the last year (the year prior since the patient's inclusion date): register confirmation and number of scheduled visits performed.
- History of asthma exacerbations during the last year (the year prior since the patient's inclusion date): register confirmation and number of asthma exacerbations.
- Use of health resources during the last year (the year prior since the patient's inclusion date): visits to emergency department (ED), visits to primary health care department, visits to specialist.
 - Nº of emergency department (ED) and hospitalization visits related to an asthma diagnosis code in the last year since the date of study inclusion.
 - Treatment prescribed at discharge: type (SABA, OCS, LABA, GCI, LTRA, Biologic, immunomodulator, others).
 - Nº of primary health care department visits related to an asthma diagnosis performed during the last year since the date of study inclusion (scheduled and unexpected),
 - Nº of specialist (allergology, physiotherapy, others) visits related to an asthma diagnosis performed during the last year since the date of study inclusion.
- Nº of oral corticosteroids (OCS) prescriptions in the last year (prior year since the patient's inclusion date).

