4. DATA ANALYSIS CONSIDERATIONS

Data analysis will be performed using SAS Enterprise Guide Version 7.15, and a statistical analysis plan will be designed and agreed before the data analysis initiation.

All the analyzes will be performed by descriptive statistical methods of all the variables separately. All the patients participating in the study who met the eligibility criteria will be included in the study population.

The quantitative data will be described by the following statistical parameters: number of valid patients (N valid), number of missing data (N missing), mean, standard deviation, median, interquartile range, minimum and maximum will also be presented.

The qualitative data will be presented through the length-frequency distributions (absolute and relative). For both cases, the following will be specified: number of observations (N) and number of missing data (N missing).

Primary objective:

To analyze the primary objectives, it will be assessed the percentage of compliance of each asthma quality care indicator established by GEMA guidelines (GEMA 4.4, Guía Española para el Manejo del Asma):

GROUP I. Diagnosis

- Diagnostic confirmation by spirometry and bronchodilator test. To know the compliance of this indicator, it will be calculated the percentage of asthmatic patients diagnosed using spirometry and bronchodilator test will be determined:

Nº patients diagnosed with asthma using spirometry x 100 / nº patients diagnosed with asthma

- Sensitization study in allergic asthma. To know the compliance of this indicator, it will be calculated the percentage of patients with a diagnosed history of suspected allergic asthma included in a sensitization study with different allergens:

Nº of patients with a diagnosed history of suspected allergic asthma included in a sensitization study with different allergens x 100 / nº patients diagnosed with asthma (and diagnosed history of suspected allergic asthma?)

GROUP II. Non-pharmacological treatment

- Smoking cessation. To know the compliance of this indicator, it will be calculated the percentage of asthmatic smokers with documented recommendations for smoking cessation:

Nº of asthmatic smokers with a documented recommendation for smoking cessation x 100 / nº asthmatic smokers

- Educational plan for patients with asthma. To know the compliance of this indicator, it will be calculated the percentage of patients included in an educational plan:

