7.2. External Expert/Health Care Professionals (Consultants & Research PIs)

APPENDIX 1. Quality assistance indicators – GEMA Guidelines

INDICATOR GROUPS	INDICATOR	CALCULATION
I. Diagnosis	1. Diagnostic confirmation by spirometry with bronchodilator test. Diagnostic confirmation of patients with asthma is performed with spirometry and bronchodilator test as an objective measure of functional involvement.	Number of patients with asthma with spirometry performed x100/number of patients diagnosed with asthma.
	2. Sensitization study in allergic asthma. Patients with suspected allergic asthma should be screened for possible sensitizations to different allergens.	Number of patients diagnosed with a history suggestive of allergic asthma with a sensitization study performed to different allergens x100/number of patients diagnosed with asthma.
II. Non-pharmacological treatment	3. Smoking cessation. Smoking cessation is recommended in smoking patients with asthma.	Number of asthma patients with smoking and registered dishabituaction recommendation x100/asthma patients with smoking.
	4. Educational plan for patients with asthma. Patients with asthma should follow a basic education program (consisting of: knowledge about their disease, about its treatment, action plan and inhalation technique, written document) as part of their treatment.	No. of asthma patients with asthma education program x100/no. of asthma patients.
III. Pharmacological treatment	5. Treatment of choice in persistent asthma. The treatment of choice in persistent asthma includes inhaled glucocorticoid (ICG) used daily. In some justified cases, leukotriene receptor antagonists may be considered as an alternative treatment.	Number of patients on control treatment for persistent asthma receiving GCI x 100/number of patients on control treatment for persistent asthma.
	6. Treatment of asthma in pregnant women. In the maintenance treatment of asthma in pregnant women, it is recommended to maintain the drugs usually used (β 2-adrenergic agonists and inhaled glucocorticoids).	No. of women with asthma who maintain their usual treatment (β 2-adrenergic agonists and inhaled glucocorticoids) in pregnancy x100/number of pregnant women with asthma on maintenance treatment.

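### Primary indicator 1 depends on a test at diagnosis that the guaranteed year of records cannot contain, and no rule says how patients with unreachable diagnoses enter the percentage

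*Combined protocol and SAP*

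**What the plan says.** **Endpoint (Section 3.3.1.1).** Indicator 1 is "Percentage of asthmatic patients diagnosed using spirometry and bronchodilator (PBD) test".

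**Data item (Section 3.3.1.2).** The matching variable is "Spirometry and bronchodilator test at diagnose".

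**Analysis (Section 4).** The formula is "Nº patients diagnosed with asthma using spirometry x 100 / nº patients diagnosed with asthma". The sentence introducing it mentions the bronchodilator test; the formula does not.

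**Appendix 1.** The calculation for the same indicator is "Number of patients with asthma with spirometry performed x100/number of patients diagnosed with asthma". It does not tie the test to diagnosis and leaves out the bronchodilator test, although the indicator's description includes it.

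**Eligibility (Section 3.2.1.1).** Criterion 3 is "Patient with asthma diagnosis more than one year before the study inclusion", with no upper limit on time since diagnosis. Criterion 4 is "Clinical data available at least 1 year before the study inclusion in the electronic medical records".

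**Observation window (Section 3.1).** "The observational period will be conformed of 12 months".

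**Unavailable items.** Section 3.3 says that "there will be the possibility in the eCRF to select the unavailability of the variables in the medical records". Section 4 reports the number missing, Section 3.4 allows 10% for unavailable data, and Section 5 names chart availability as the main limitation.

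**The concern.** Criteria 3 and 4 together mean that the one guaranteed year of electronic data contains no eligible patient's diagnosis. Whether the diagnostic work-up can be seen depends on how much further back each chart goes, and the plan neither requires nor records that.

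Two kinds of patient then become hard to tell apart: those whose chart does not reach the diagnosis, and those whose chart reaches it but shows no test. Only the second says anything about quality of care. The Section 4 denominator, read literally, counts both as non-compliant. If both are instead marked unavailable and dropped, true failures leave the denominator too. The first route pushes the percentage down and the second pushes it up, and the plan does not choose. Because Appendix 1 also uses a different numerator, the same primary indicator could be reported as several different percentages from the same charts.

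**Working it through.** **1. The plan's own figure.** Section 3.4 gives a proportion of 50%, a margin of ±6 points, 95% confidence and 10% unavailable.

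- n = 1.96² × 0.5 × 0.5 / 0.06² = 266.8, rounded up to 267. This matches.
- 267 / 0.9 = 296.7, so 297. The stated 300 is consistent with rounding up.

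The sample size is correct for its inputs. The question is whether its single overall 10% allowance suits this indicator.

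**2. How many can be unavailable before ±6 is lost.** 300 − 267 = 33, and 33/300 = 11%.

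**3. If uncovered patients are set to missing.** Let u be the share whose record does not cover the diagnosis. The documents do not give u, so the values are assumptions. Half-width at 50% = 1.96 × √(0.25 / (300(1 − u))).

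| u | evaluable n | half-width (points) |
|---|---|---|
| 10% | 270 | 5.96 |
| 20% | 240 | 6.33 |
| 30% | 210 | 6.76 |
| 50% | 150 | 8.00 |

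**4. If uncovered patients count as not done.** Assume also that record depth is unrelated to whether the test was done. The expected estimate is then p(1 − u), where p is the true percentage. For an assumed p = 80%:

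- u = 10%: 0.80 × 0.90 = 72%
- u = 30%: 0.80 × 0.70 = 56%
- u = 50%: 0.80 × 0.50 = 40%

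**5. If 'unavailable' also absorbs real failures.** Suppose uncovered patients are dropped, and a share w of covered patients with no test found is marked unavailable as well. The estimate becomes p / (p + (1 − p)(1 − w)). For p = 80% and assumed w:

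- w = 10%: 0.80 / (0.80 + 0.18) = 81.6%
- w = 30%: 0.80 / (0.80 + 0.14) = 85.1%
- w = 50%: 0.80 / (0.80 + 0.10) = 88.9%

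So the error can go either way.

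**6. What bounds would show.** Count uncovered patients first as all failures, then as all successes.

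- u = 10%, p = 80% among covered: 216 of 270 compliant. Bounds are 216/300 = 72% and (216 + 30)/300 = 82%.
- u = 30%, p = 80% among covered: 168 of 210 compliant. Bounds are 168/300 = 56% and (168 + 90)/300 = 86%.

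The bounds are exactly u wide.

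**The case against.** The strongest reply is that the plan already allows for this. Criterion 4 sets a minimum record length, and nothing caps look-back. Section 3.3.1.2 states a one-year window where it wants one (SABA and OCS counts, visits, exacerbations) and states none for age at diagnosis, spirometry at diagnosis or the sensitization study. The natural reading is that those items are sought in the whole chart. The unavailable option, the reporting of missing numbers and the 10% allowance make missing the likelier route than failure. At 10% unavailable the precision target is met (5.96 points). At a true 80% the half-widths are narrower: 1.96 × √(0.16/270) = 4.8, 1.96 × √(0.16/210) = 5.4 and 1.96 × √(0.16/150) = 6.4 points for u = 10%, 30% and 50%. Details are also deferred to a later SAP and a data management plan.

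Most of this stands, and it rules out a stronger reading. A reader might infer that old diagnoses will as a rule be scored as failures or lost, so that indicator 1 measures the age of the record and not the quality of diagnosis. The documents do not support that. The problem touches only patients whose chart does not reach the diagnosis, and their share is unknown.

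What the reply does not supply is a rule. An unavailable flag records a gap without saying whether the patient stays in the denominator, and it does not say why the item is unavailable. A later SAP can set the denominator, but it cannot recover a distinction that was never collected.

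A reader might also want to solve the problem by making Appendix 1's spirometry-performed count the primary figure. That would credit a later follow-up test as diagnostic confirmation, and it would still fail a patient tested only before the electronic record began.

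**Conclusion.** The point holds as a gap in definition and data capture for one primary indicator. The documents establish that the test is tied to the diagnosis, that every diagnosis lies outside the guaranteed year of data, that the literal denominator is all diagnosed patients, and that no passage says how an unreachable diagnosis enters the percentage.

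The size depends on u, which is unknown. Counting uncovered patients as not done lowers the result by p × u: 8 points at p = 80% and u = 10%, 24 points at u = 30%, provided that record depth is unrelated to testing. Setting them to missing keeps ±6 points at 50% only while 33 of 300 or fewer are unavailable. The values of p, u and w are illustrations, not estimates for this site. The sample size calculation itself needs no correction.

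**What to change.** 1. Add one yes/no eCRF item: does the available record cover the diagnosis date? Add it before chart abstraction starts, since recovering it later could mean re-reading up to 300 charts.
2. Calculate spirometry plus bronchodilator test at diagnosis among patients with yes. Show that denominator and the number not covered. State that a covered chart with no test found counts as not done.
3. Report the bounds over all patients, with uncovered patients counted as all failures and then as all successes.
4. Report Appendix 1's spirometry-performed percentage as a separate, labelled supportive figure, not as the replacement primary.
5. Reconcile the wording of Sections 3.3.1.1, 3.3.1.2 and 4 and Appendix 1, including whether the bronchodilator test is required in the numerator, and state the look-back for this item.

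**Cost.** One eCRF item and a few lines of SAP text. The at-diagnosis figure will have a smaller denominator and a wider interval. It describes covered patients, who are likely to be those diagnosed more recently; the bounds keep that limitation visible.
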